#### 4.5.2. Variables

We will consider a range of **patient outcome variables**. Our primary patient outcome is mortality within 30 days of admission, as it has a strong association with staffing levels.(5, 17) Other patient outcomes we will model include length of stay, readmissions within 30 days (which both have high strength of evidence for an association with staffing levels according to a recent review)(4) and healthcare-associated conditions such as pneumonia and pressure ulcers (which have moderate evidence).(4) We will limit the latter analyses to surgical patients since for medical patients it is harder to distinguish between complications and conditions present on admission.

Our other outcomes are measures of **perceived staffing adequacy** assessed through the prospective micro-survey. We will ask clinical nurses three questions as in our previous study: i) Were there enough staff for quality?, ii) Were breaks missed? and iii)Was care left undone?(13) These were derived following pilot work of a more extensive set of questions, and are aimed to be quick to answer and give a good indication of overall staffing adequacy on a ward. In our previous study these were all associated with deviation from SNCT-recommended staffing.(13)

Ethics/ERGO no: 100780; IRAS no: 346148

Our **independent variables** are the deviation of actual staffing from measures of staffing required. In other words, under-/over-staffing compared to different measures of what is needed. Actual (achieved) staffing is measured as total care hours per patient day and includes all nursing staff on the ward: both Registered Nurses and Support Workers, both permanent and temporary (bank or agency) staff. Required staffing will be measured in different ways including: using the SNCT, current ward establishments, algorithmic measures (including the ward-level and patient-level approaches).

To start with we will model overall staffing but where possible will also consider **skill mix** by splitting out staff groups. We will use current ward establishments to calculate the planned skill mix and apply these to our alternative measures of staffing requirements. This will allow us, for example, to assess Registered Nurse understaffing and Support Worker understaffing separately, which is important since differing relationships have been found with patient outcomes.(5) We will use the pay band to categorise staff, given the differences in roles and job titles between Trusts.

#### 4.5.3. Data analysis

This workstream will involve further **data linkages**. For each ward and shift or 24-hour period, we will calculate the actual staffing and the staffing requirements according to the most promising algorithms, as well as according to the SNCT. These will be converted to care hours per patient day. This requires working out which staff shifts and which patient stays overlap with each time period, as well as calculating the staffing requirements based on patients on the ward in each period. Then for each patient admission, we will link the understaffing/overstaffing they experienced during their hospital stay with their outcomes. Separately for each period we will link ward understaffing/overstaffing with measures of perceived staffing adequacy (from the micro-survey).

We will use **regression modelling** to assess the relationship between deviation from staffing requirement (measured in different ways) and outcomes. Depending on the nature of the outcome variable we will fit the appropriate model type (e.g. survival model for mortality, logistic regression for hospital-acquired conditions and perceived staffing adequacy). Our longitudinal data will allow us to explore how staffing over a patient's stay affects outcomes, since effects of low staffing may accumulate; we will consider approaches such as moving averages and exponentially weighted moving averages.

We will assess intra-cluster correlation coefficients to see whether there are unmeasured differences between wards. If appropriate, we will use multi-level regression models to assess how relationships differ between wards and hospitals, which can be used as an indicator of good/poor fit of a staffing measure, as in our previous work.(52) Specifically, random intercepts models can help us estimate, for each ward, the probability of the nurse in charge reporting enough staff for quality when staffing matches the measured staffing requirement. On the other hand, random slopes models can indicate for which wards relationships are in the same/opposite direction to what is expected.

We will compare how well different measures of staffing requirements appear to capture workload according to Akaike Information Criterion **model fit.** We will also compare the benefits of using alternative staffing requirement measures by using decision analytic methods like **decision analytic curves**, as deployed in research about the Rafaela staffing tool.(26) The advantage of this method is that it provides an estimate of net benefit without requiring additional data on costs or quality-adjusted life years.(53)

Ethics/ERGO no: 100780; IRAS no: 346148

We will investigate the impact of changing our modelling approach and assumptions through **sensitivity analyses**, for example varying the exposure window and fitting alternative model types. We will also run subgroup analyses to understand the fit for particular patient groups.

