#### 3. Aims and objectives

This study aims to develop a method to measure demand for nursing staff on hospital wards using routine data, to facilitate establishment planning, to monitor staffing adequacy/safety in real-time and to inform safe and efficient deployment of staff. To achieve this we have a number of objectives:

- 1) understand what works and does not work for nurses and nurse managers when using staffing tools, and incorporating this into the design of an algorithm for estimating staffing requirements
- 2) develop statistical/machine learning algorithms to estimate nurse staffing requirements from routinely available patient data, starting with replicating Safer Nursing Care Tool assessments
- 3) assess the validity of algorithms by determining whether staffing below the estimated staffing requirements is associated with adverse patient outcomes/ nurse perceptions of inadequate staffing.

Throughout the study we will engage with patients and the public to understand their experiences of hospital nurse staffing and implications for our algorithm development.

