## 4.5. Workstream 3: Validating measures of nurse staffing requirements against patient outcomes and nurse perceptions of inadequate staffing

We will conduct a retrospective observational study to investigate the associations between actual under/over-staffing relative to each candidate measure of staffing requirements and a range of outcomes. One would expect that as staffing increases relative to a measure, the risk of poor patient outcomes and perceptions that staffing is inadequate decreases.(13, 26) In the absence of a gold standard, we will compare model fit against models with staffing requirements measured by the SNCT, as well as against the current ward establishments where possible. For this we will use routine data extracted from hospital IT systems along with an empirical (prospective) micro-survey of nurses (three tick-boxes) to understand perceptions of staffing adequacy.

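### Workstream 3 ranks staffing measures by raw AIC, which gives no uncertainty for the algorithm-versus-SNCT difference, so measures that are exactly equal will regularly look ranked

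*Protocol*

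**What the plan says.** Protocol section 3 sets the validity objective: "determining whether staffing below the estimated staffing requirements is associated with adverse patient outcomes/ nurse perceptions of inadequate staffing". The opening of 4.5 makes SNCT the benchmark in the absence of a gold standard: "we will compare model fit against models with staffing requirements measured by the SNCT". Current ward establishments are a second comparator where possible.

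Section 4.5.3 gives the criterion: "We will compare how well different measures of staffing requirements appear to capture workload according to Akaike Information Criterion". It adds decision curves, and it offers random-intercept and random-slope models as further indications of fit.

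The competing measures are plural. Section 4.5.3 calculates "the staffing requirements according to the most promising algorithms, as well as according to the SNCT", and 4.5.2 lists "algorithmic measures (including the ward-level and patient-level approaches" among them. Their number is not fixed.

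On outcomes, 4.5.2 states: "Our primary patient outcome is mortality within 30 days of admission". It continues: "Other patient outcomes we will model include length of stay, readmissions within 30 days". Healthcare-associated conditions follow, with two examples. Three micro-survey items on perceived adequacy form the second family and are not ranked among themselves.

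**The concern.** AIC puts models in order. It does not say whether the gap between two of them is larger than sampling variation would produce. The measures compared here are non-nested: each enters as its own deviation of actual from required staffing. If the models are otherwise the same, they have equal numbers of parameters. The AIC penalty then cancels, and the ranking is simply a ranking of log-likelihoods. One of two equal measures must come out ahead.

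The informal convention that a gap of 2 units means something does not help. It is not a standard error for a non-nested difference, and the spread of that difference grows with the number of rows.

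At stake is how a finding such as better fit than SNCT, or fit as good as SNCT, should be read. Section 5 makes further funding depend partly on correspondence with the patient and staffing-adequacy outcomes, and section 4.3.1 takes algorithms developed and validated in Workstreams 2 and 3 into the later workshops. A bare rank is weak support for either step.

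**Working it through.** **The plan's own sample size (Sample sizes, under 4.5).**
- Low: 30 days x 2 reviews x 20 wards = 1,200 ward-days per Trust.
- High: 0.85 x (0.75 x 365) x 20 = 4,653.75, stated as 4,653.
- Five Trusts: 5 x 1,200 = 6,000 and 5 x 4,653 = 23,265. Both totals reproduce.

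**Outcomes (4.5.2).** 1 (mortality) + 2 (length of stay, readmission) + at least 2 (conditions) + 3 (survey items) = at least 8.

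**Raw AIC with equal measures.** With equal parameter counts,

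AIC(SNCT) - AIC(algorithm) = 2 x [logL(algorithm) - logL(SNCT)].

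If K algorithms and SNCT are exchangeable, SNCT ranks first on one outcome with probability 1/(K+1). Some algorithm therefore ranks above it with probability K/(K+1):
- K = 1: 1/2 = 50%
- K = 2: 2/3 = 67%
- K = 4: 4/5 = 80%

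These apply to mortality alone as much as to any other outcome. Naming one outcome does not by itself cure the problem.

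Over three outcomes with independent fit differences, the chance of at least one algorithm win is:
- K = 1: 1 - (1/2)^3 = 87.5%
- K = 2: 1 - (1/3)^3 = 1 - 1/27 = 96.3%

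**Simulation of the AIC comparison.** All settings here are assumptions, because the protocol gives no number of algorithms, effect size or error correlation.
- True need T is N(0,1); actual staffing is 0.5T + N(0,1).
- SNCT and two algorithms each equal T plus error of SD 0.5, so they are exactly equally accurate.
- Error correlation runs from 0 to 0.8. A high value shared with SNCT is plausible because the algorithms are trained on SNCT.
- Three binary outcomes are logistic in (staffing - T), slope -0.1 to -0.5, with a shared random term.
- There are 6,000 to 23,000 rows. Each measure is fitted in its own logistic regression and AIC is compared.

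| Event (2 equal algorithms, 3 outcomes) | Share of runs |
|---|---|
| Some algorithm has lower AIC than SNCT on some outcome | 91-97% |
| Some such win exceeds 2 AIC units | 51-97% |

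The first row agrees with the 96.3% above. The low end of the second row comes from a shallow slope, high shared error and the smaller sample. With one algorithm and one outcome, the algorithm had the lower AIC in about 43-54% of runs. At 150 runs per setting the Monte Carlo standard error is at most sqrt(0.25/150) = 4.1 percentage points, so the ranges are approximate. Rows were independent; ward clustering would add noise to the ranking.

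**With an interval.** If a win on a single prespecified comparison requires the lower limit of a two-sided 95% interval to exceed zero, an equal algorithm wins 2.5% of the time by construction, against 50% on raw AIC. The interval does most of the work; naming the outcome does less.

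**The case against.** The strongest reply is that a protocol may leave comparison margins and an outcome hierarchy to an analysis plan, and that plan is not shown. This largely stands. The absence of a full hierarchy is no finding. What remains is that the protocol itself selects raw AIC as the yardstick, and that choice can mislead if followed literally.

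Four stronger readings are tempting, and the documents do not support them.

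- **A single win would be declared success.** A reader might infer this from the slash joining the two outcome families in section 3. No passage says so. Section 5 joins the families with *and*, and the opening of 4.5 expects both poor patient outcomes and perceived inadequacy to fall as staffing rises. The any-win percentages therefore describe how unstable the rankings are, not the error rate of a rule the protocol adopted.
- **There is no primary outcome.** There is one: 30-day mortality among patient outcomes. The unranked part is the set of three survey items.
- **Worse algorithms would usually win too.** The result is for algorithms equal to SNCT. One algorithm worse by 2 standard errors of the fit difference on every outcome would win on at least one of eight in only 7-17% of cases, for correlations between outcomes of 0.8 down to 0.
- **Type I error is inflated.** The protocol states no alpha for these comparisons, so no such rate can be attributed to it.

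It is also fair that the first aim is to replicate SNCT and save nursing time, so beating SNCT is not the sole headline. That makes a claim of being as good as SNCT more likely, and AIC rank cannot support that claim either. Finally, restricting Workstream 3 to one algorithm would discard planned comparisons: some Trusts can support only the ward-level approach, and different decisions need different predictors. The remedy should not require it.

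**Conclusion.** The point holds as a limitation of the comparison method in 4.5.3. Raw AIC ranking gives no uncertainty for the algorithm-minus-SNCT difference. An equal algorithm leads about half the time on any one outcome, and with two equal algorithms and three outcomes a win of more than 2 AIC units appears somewhere in about 51-97% of runs.

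The half follows from symmetry alone. The 51-97% rests on the assumed slopes, error correlations, two algorithms and independent rows. The size of the AIC gaps depends heavily on those assumptions, so no single gap should be quoted as typical.

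This does not show that the study would make a false claim. It is a worthwhile, inexpensive improvement, not proof of an error in the plan.

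**What to change.** In 4.5.3, or in the analysis plan with a reference from there:

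1. Report each algorithm-minus-SNCT difference in fit with an interval obtained by resampling whole wards, on rows where both measures are available. Base any statement of better fit on that interval, not on AIC rank.
2. If an algorithm is to be described as good as SNCT, state the margin in advance.
3. Read the comparison first on 30-day mortality, already primary, and on one survey item named in advance.
4. Choose the algorithm or algorithms on Workstream 2 agreement before Workstream 3 outcomes are linked. Several may still go forward.
5. Present the remaining outcomes, decision curves and random-slope readings as supporting.

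The cost is a few sentences and a bootstrap, with no new data. For mortality, a rule is needed for assigning admissions that cross wards to one resampling unit. The downside is that some apparent AIC advantages will have to be reported as inconclusive.

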#### 4.5.4. Equality, Diversity & Inclusion

Equality, Diversity and Inclusion are key aspects that we will consider in each workstream. In particular, we will consider these when engaging staff and patients in workshops, and when developing and validating algorithms. We will gather information about protected characteristics from participants in workstream 1 workshops through an optional online anonymous form, with the results stored in an access-restricted secure electronic file-store area. For workstreams 2 and 3, since we are using routinely collected data, we will have access to information to derive only some of the protected characteristics (sex, age band and partial information on disability and pregnancy/maternity).

When working with staff and patients in workshops (workstream 1 and PPI), our main goal is to **remove barriers to access** to achieve meaningful engagement, and we plan to do so by:

- 1) Organising workshops in a choice of online or in-person formats, following best practice to ensure all participants get equal opportunities to co-create and give feedback: i) Accessing relevant technology e.g. "owl" microphones/cameras for those attending in-person; ii) Avoiding running meetings for longer than 90 minutes, iii) If group work is required, ensuring participants online can participate meaningfully in a breakout room and report back; iv) Ensuring all workshop materials and agenda are available in advance to all, especially online participants.
- 2) Planning workshops at times of the day that might fit our intended participants e.g. active members of the nursing workforce might not be available during standard work hours. We will also reimburse patient-facing nurses for their time since they do not have research time in their role. We will also consider childcare commitments and pay for childcare to allow participants to attend. Similarly we will cover costs of carers or personal assistants in line with NIHR payment guidance.
- 3) Actively recruiting people from a variety of backgrounds e.g. ages, ethnicities and socio-economic backgrounds. We will do this by: emphasising that we want views from a diverse group of individuals when we advertise and potentially targeting particular groups who tend to be underrepresented, through support groups such as Equality 4 Black Nurses or the Imperial Health Charity, or cultural groups such as the African Women's Forum in Portsmouth.

In workstreams 2 and 3 we are analysing data on all patients staying on inpatient wards, so there is no bias introduced from recruitment methods. However, there are other EDI considerations, particularly around potential **algorithm biases** which can arise at different points in the algorithm building cycle, for example when models are trained on unrepresentative data sets(54). We will consider potential biases at each stage of the algorithm building cycle.

For example, we will minimise the risk of **representation bias** arising by using data from hospitals serving diverse populations. Although in our datasets we will not have access to data on ethnicity or socio-economic status, so cannot specifically check how well algorithms work for particular groups, we aim for our datasets to cover diverse populations, for example the patient population served by Imperial hospital serves a relatively high proportion of people from ethnic minorities(55) and Portsmouth has a

relatively high proportion of people of low socioeconomic status.(56) However, as well as making efforts to include data from under-served groups in our analysis, we shall specifically examine the performance of our algorithms in wards with high numbers of patients from under-served groups such as the over 75s, those with learning disabilities and those with mental health conditions. If the performance (predictive accuracy or validity when assessed against patient/staffing adequacy outcomes) is poorer in these wards then we shall investigate if there are important variables missing that could affect nurse staffing requirements. To understand this, we will engage with our patient and nurse representatives.

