# 4.4. Workstream 2: Developing measures of nurse staffing requirements based on routine data

This workstream aims to **develop and test algorithms** to estimate nurse staffing requirements from routinely available patient data. Since there is no "gold standard" for measuring nurse staffing requirements, in the first instance we will aim to replicate measurements using the NICE-recommended Safer Nursing Care Tool, which is in use in most English hospitals. This tool bases its estimates on a categorisation of patients on the ward into acuity/dependency groupings, with estimates of direct care time for these patients as well as allowances for other work associated with patients (indirect care) and other administrative tasks. Adjustments to account for differences in this allowance are currently left to professional judgement. We will extend our approach to attempt to capture some of these workload aspects beyond acuity/dependency, while recognising that not all elements of work are measurable.

We will develop two broad approaches using data that is already recorded to replicate the results of SNCT assessments: i)replicate **individual** patient acuity/dependency classifications and ii) replicate the staffing requirements for a **whole ward**. For i), where Trusts record individual SNCT ratings we will seek to develop models based on rich individual data from electronic patient records and care plans. However, given that staffing decisions are generally made based on the whole ward as nurses care for several patients each, we will also aggregate these to a ward level (ii). It is possible that inaccuracies in individual categorisations may have little impact on overall estimates when aggregated to a ward level. Furthermore, some Trusts record only counts of patients per SNCT category,

Ethics/ERGO no: 100780; IRAS no: 346148

which cannot be linked to individuals, so for these Trusts we can only follow approach ii) and estimate ward staffing requirements directly.

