#### 4.4.2. Sample sizes

For **developing the algorithms**, we will use retrospectively collected data from our two partner Trusts. Since the new version of the SNCT launched in October 2023, we will extract data from this date onwards or from when the new tool was embedded in the Trusts. We aim to collect at least one year of data. This covers two staffing establishment reviews where acuity/dependency scores are recorded for at least 30 days, so there will be a minimum of 60 (30 x 2) days' data per ward, although in many wards they collect data much more frequently giving about 730 (2 times per day x 365) data points per ward. Scaled up across wards and two Trusts this will give us in the region of 4,800-58,400 ward shift data points for the ward-level approach (assuming 40 wards per Trust), and approximately 120,000-1,460,000 patient shift data points for the patient-level approach (assuming on average 25 patients per ward). For **external validation** of the algorithms, we will use data from at least three further Trusts, and more recent data from our two partner Trusts (data covering at least 1 year).

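### The only algorithm-bias check that names the under-served groups is made by ward, which dilutes a patient-level error by the group's share of the ward; add a patient-level check where individual ratings exist

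*Protocol*

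**What the plan says.** Protocol section 4.5.4 (Equality, Diversity & Inclusion) sets the check. The team will "examine the performance of our algorithms in wards with high numbers of patients from under-served groups", with the groups given as "such as the over 75s, those with learning disabilities and those with mental health conditions". Performance there means predictive accuracy, or validity against patient and staffing-adequacy outcomes. The consequence is also tied to the ward: if performance "is poorer in these wards then we shall investigate if there are important variables missing". The same section limits which characteristics can be used: "we will have access to information to derive only some of the protected characteristics (sex, age band and partial information on disability and pregnancy/maternity". It states that ethnicity and socio-economic status will not be available.

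Section 4.4 plans a patient-level approach, conditionally: "where Trusts record individual SNCT ratings we will seek to develop models based on rich individual data". Trusts that record only counts per SNCT category can be analysed only at ward level. For the patient-level approach, section 4.4.4 links each admission's data to the patient's acuity/dependency category at every assessment. Section 8 confirms individual-level linkage, inside secure data environments.

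Section 4.5.3 separately promises subgroup analyses of fit for particular patient groups, in Workstream 3. It names no groups.

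**The concern.** The purpose of the check is to find out whether the algorithm misjudges the needs of certain patients. Its unit is the ward, so it sees a blend of those patients and everyone else there. Random errors in individual ratings tend to cancel on aggregation. A systematic error in one group does not cancel, but it is averaged over all the patients on the ward. Section 4.4 itself expects inaccurate individual categories to matter little after aggregation. That helps a staffing estimate but weakens a bias check.

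If the ward comparison looks clean, the search for missing variables does not start. A group that is rare and spread thinly across wards could then be under-predicted throughout with nothing in the planned check to show it. Where a Trust's individual ratings are linked to patient records, the error in that group could be measured directly.

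**Working it through.** **Inputs from the protocol (section 4.4.2).** "assuming on average 25 patients per ward"; "assuming 40 wards per Trust", two development Trusts; "there will be a minimum of 60 (30 x 2) days" of data per ward, rising to about 730 data points where ratings are made twice daily.

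**The protocol's own figures reproduce.**
- Ward shifts: 60 × 40 × 2 = 4,800 and 730 × 40 × 2 = 58,400.
- Patient shifts: 4,800 × 25 = 120,000 and 58,400 × 25 = 1,460,000.

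**Inputs that are assumed.** The protocol gives no group shares, size of bias or error SDs. I take a bias b = 20% of mean per-patient need for each patient in the group, no bias in others, and the shares shown in the table.

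**Dilution.** With group share p, the ward's per-patient requirement shifts by p × b.
- 1 patient in 25: 0.04 × 20% = 0.8%.
- 3 patients in 25: 0.12 × 20% = 2.4%.

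**Contrast between wards.** High-share wards minus other wards shows (p_high − p_other) × b. The fraction of the bias kept is p_high − p_other, whatever the value of b.

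**Effect on RMSE,** one of the statistics named in section 4.4.4. The ratio of ward RMSE, high-share to other wards, is √(s² + (p_high b)²) / √(s² + (p_other b)²), where s² = (patient error SD)²/25 + (ward error SD)². The assumed patient error SD is 20% or 35%; the assumed ward error SD is 0, 5% or 10%. One case, with patient SD 20%, ward SD 0 and shares 12% vs 1%: s = 0.20/5 = 0.04, and √(0.0016 + 0.000576) / √(0.0016 + 0.000004) = 1.165.

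| Assumed group and shares (high-share vs other wards) | Shift in high-share wards | Contrast seen | Bias kept | RMSE ratio (range) |
|---|---|---|---|---|
| Learning disability, 4% vs 1% | 0.8% | 0.6% | 3% | 1.00-1.02 |
| Learning disability, clustered, 12% vs 1% | 2.4% | 2.2% | 11% | 1.02-1.17 |
| Mental health condition, 30% vs 10% | 6% | 4% | 20% | 1.10-1.61 |
| Over 75s, 60% vs 30% | 12% | 6% | 30% | 1.26-1.75 |
| Over 75s, older people's ward, 90% vs 30% | 18% | 12% | 60% | 1.60-2.56 |

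For mental health conditions at 20% vs 10%, the contrast is 2% and 10% of the bias is kept.

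**Patient-level comparison.** Mean signed error within the group estimates b itself, here the full 20%, with no dilution. If only one partner Trust holds individual ratings (an assumption), it contributes half the patient shifts, 60,000-730,000. A group at an assumed 1% then supplies 600-7,300. These include repeated ratings of the same patients on the same wards, so the effective number is smaller and intervals must allow for clustering.

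**The case against.** - **Patient subgroups are already planned.** Section 4.5.3 commits to them, so a reader who infers that patient groups are never examined except through wards goes too far. That commitment sits in Workstream 3, concerns fit of the outcome models, names no groups, and does not mention agreement with SNCT ratings or the trigger in section 4.5.4. It softens the gap without closing it. A statistical analysis plan may name the groups, but the unit and trigger of the bias check are already fixed in the protocol.
- **The ward is the right unit for staffing.** Section 4.4 says staffing decisions are generally made for whole wards, and the micro-survey outcomes exist only per ward and period. This stands, and is why the ward check should stay. It does not make the ward a good unit for detecting error in a patient group, and patient-level classification is itself a planned output.
- **The data may not be there.** Individual ratings exist only where Trusts record them, disability information is partial, and section 10 lists secure data environment approval as still to be obtained. A reader might infer that ratings are held for every patient; the protocol does not say so. The remedy has to be conditional.
- **The reference is imperfect.** Patient-level error treats the SNCT rating as the standard, although section 4.4 says there is no gold standard. Bias within the SNCT would go unseen. Signed error by group can also vary with specialty, which clustering does not adjust for. Both limits stand.
- **The magnitudes are assumed.** They are. The direction, and the formula for the fraction kept, do not depend on the chosen bias.

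**Conclusion.** The point holds in a limited form. The one check that names the under-served groups is set, and triggered, at ward level. A patient-level bias enters it multiplied by the group's share of the ward. On the assumed shares, the ward contrast keeps about 3-11% of the bias for a rare group such as learning disability, about 20% for mental health conditions (30% vs 10%) and about 30-60% for over 75s.

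A reader might infer that the check is blind for all three groups. The arithmetic does not support that: over 75s can form a large part of a ward, and a 20% error would remain visible there. The risk of false reassurance lies mainly with rare, dispersed groups. The conclusion rests on 25 patients per ward from the protocol, on assumed shares and error SDs, on equal bias across a group's members and on none in other patients.

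**What to change.** In section 4.5.4, for Trusts where individual SNCT ratings are recorded and linked:

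- Report mean signed error (predicted minus SNCT multiplier) and category agreement by patient group: age over 75, sex, and learning disability and mental health condition as far as recorded.
- Give intervals clustered by ward.
- State that poorer performance in a patient group, as well as in a ward, triggers the search for missing variables.
- Keep the ward-level check for Trusts with counts only and for the staffing-adequacy outcomes.
- Say whether the section 4.5.3 subgroup analyses include these groups.

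The cost is a few extra tables in the secure data environment. Rare groups will give small cells, some lost to the small-number suppression already planned in section 8. Incomplete disability recording will leave some group members unidentified. The report should say that the SNCT rating is a reference and not a gold standard.
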